Data analysis will be performed in multiple stages. In the initial stage, preliminary analyses will be performed by examination of the distribution of variables to assess their characteristics (means, standard deviations, and skewness). Descriptive statistics and graphs will used to summarize the characteristics of the study population. Continuous measures will be tested for normality and homogeneity of variance. Non-normally distributed variables will be transformed to meet the normal distribution assumption for linear models. Randomization will be assessed by performing a series of Wilcoxon-rank sum tests, Chi-square or Fisher's exact tests to compare the groups on demographic and initial baseline clinical variables. Any variables on which the groups differ initially will be explored as covariates in subsequent analyses, and we will take this into account in the interpretation of the outcome. At the second stage, we will perform sensitivity analyses for the impact that potentially informative missing data may have on the analyses. We will use pattern-mixture models to assess if there is bias due to drop out or missing data. In addition, we will consider the extension of the pattern-mixture model, which allow subject-to-subject heterogeneity.

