At the final stage, hypotheses will be tested using Mixed Effects models, a generalized linear model described by Gibbons et al.⁹¹, Hedeker et al.⁹² and Laird et al.⁹³. Responses at baseline, throughout treatment (sessions 7, 13, 21), post treatment (session 26), 3- and 6-month follow-up will be nested within subjects. Intercept and slope will be modeled as random effects nested within subject; Treatment group, time, and group-by-time interaction will be a fixed effect. A fully saturated treatment by time model will be utilized for inference. Co-variance structure will be chosen based on Akaike's Information Criterion (AIC). Data will be analyzed from all randomized subjects on whom we have a baseline assessment and at least one post-baseline evaluation. If it is needed based on analyses on stage one, baseline covariates (e.g., demographics) will also be added to the model. All hypothesis tests will be intent-to-treat, and will be two-sided at the .05 level. We will adjust p-values for multiple testing within each hypothesis separately by using a Bonferroni correction whenever more than one variable is being tested. Although we didn't have any drop-out in out pilot study, we included a drop-out rate of 10% after the baseline assessment but prior to the first post-baseline evaluation in our power analyses.

Hypothesis 1.1-1.3: Relative to those assigned to ET alone, CREST participants will show significant reduction in **hoarding severity** (primary outcome), improvement in **functioning** (both functional capacity and self-reported functioning; secondary outcomes) and improvement in **quality of life** over time.

- Independent Variables: Treatment Groups (CREST and ET), Time points (baseline, throughout treatment (sessions 7, 13, 21), post-treatment (session 26), 3 and 6-month follow-up).
- Dependent Variable: Hoarding severity (SI-R), Functioning (UPSA, USORT, SLOF, WHODAS 2.0.), Quality of Life (Neuro-QOL).

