- Statistical Analysis: The dependent variable will be analyzed by mixed effects model methods as described above. Baseline demographic and other clinically important characteristics at baseline will be assessed for imbalance between the two groups and their association with the outcome using a univariate analysis. Those found to be significantly unbalanced between intervention groups (p < 0.10) and moderately associated with the outcome (p < 0.15) will be included as covariates in the model. We will adjust p-values for multiple testing within each hypothesis separately by using a Bonferroni correction whenever more than one variable is being tested

Hypotheses 2.1: Treatment adherence, improvement in executive functioning, and reduction in avoidance will mediate hoarding symptom reduction in CREST.

Dependent Variables: Hoarding severity (SI-R)

Independent Variables: Executive Functioning (D-KEFS scaled scores and PCET), Avoidance (AAQ and BAT) and Treatment Adherence score.

Statistical Analysis: The effect of mediator variables will be tested following the procedures recommended by Kraemer⁹⁴, Bauman⁹⁵, Cohen and Cohen⁹⁶, and Busemeyer and Jones⁹⁷. Briefly, treatment mediators explain how or why one variable affects the treatment effect and are defined as mechanisms through which a treatment might achieve its effects. The mediator's effect is measured during the treatment and is correlated with treatment choice and may possibly be a result of treatment and have either a main or interactive effect on the outcome. The dependent or outcome measure (SI-R) will be evaluated throughout the study and will be used as a repeated measure for all the available time points. In essence, the slope of each outcome measure on time will be used as a dependent measure. The mediator and bootstrap technique will be used to calculate a 95% confidence interval for mediation effect. Random effects models will be used for analysis and the change score of mediators will be included in the model.

Hypotheses 2.2: Symptom severity reduction and improved functional capacity will mediate improved quality of life in CREST.

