Power analyses are performed for all hypotheses, incorporating the longitudinal nature of the design. Within this design, repeated observations within subjects are potentially correlated. This has a profound impact on the resulting tests of significance⁹⁸. When the within subject correlation is properly incorporated, the repeated measures analysis takes full advantage of all information obtained from each subject, thereby greatly increasing statistical power over methods that compare treatments cross sectionally⁹⁹. Using the method described by Diggle, Liang, & Zeger¹⁰⁰ and Ahn et al.¹⁰¹, power calculations can be made for repeated measures designs under specified assumptions. Hedeker, Gibbons, & Waternaux¹⁰² extend Diggle et al.¹⁻³'s method for various covariance structures. Procedures describes by Hedeker et al.¹⁰² for Random Regression Models which incorporated these principles was used for the proposed study to estimated needed sample size (RMASS program provided by Hedeker for the Random Regression Model). The design assumptions consist of a 2 treatment groups and up to 7 visits (baseline, sessions 7, 13, 21, 26, and 3- and 6-month follow-up) where the slope is the dependent measure. Other assumptions used were alpha-level, nature of the hypothesis (two-sided versus one-sided), drop-out rate, and variance-covariance matrix of the longitudinal data. We assume a Type-I error level (alpha-level) of .01 to 0.05, drop-out rate of 15% and an autoregressive covariance structure. Data reported in the preliminary studies section which included our own pilot studies were used to calculate effect sizes. From the preliminary analysis of pilot study, the estimated standard deviation (SD) for SI-R score ranges from 12.75-12.82 and the between visit correlation coefficient of 0.71. We considered a range of estimates of stand deviations of 12.5, 12.8 and 13.0, and correlations of .45 to 0.70 in our power analysis. We have reported large effect sizes of 1.02 and 1.51 from our previous studies which converted to differences of 60 to 37 for our primary outcome. However, for these calculations, we conservatively selected smallest clinically meaningful differences that we would like to be able to detect. This was then converted to a medium effect size, defined mathematically as a between-group difference increasing linearly from 0 at baseline to .5 SD units at the last time point. Calculations using the above assumptions indicated that the study will have minimum power of 80% to yield a statistically significant result for a medium effect size with the proposed sample size of 136 patients (68 for each of the two groups).

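### Baseline covariates added as main effects cancel out of the group-by-time effect, so the planned imbalance adjustment does not act on Hypothesis 1

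*Combined protocol and SAP*

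**What the plan says.** All of the relevant text is in the Statistical Plan and the Power Analysis of the combined protocol and SAP.

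- **Responses (final stage).** "Responses at baseline, throughout treatment (sessions 7, 13, 21), post treatment (session 26), 3- and 6-month follow-up will be nested within subjects". Baseline SI-R is therefore part of the outcome vector.
- **Fixed effects (final stage).** "Treatment group, time, and group-by-time interaction will be a fixed effect", and "A fully saturated treatment by time model will be utilized for inference". The arms are free to differ at baseline.
- **Effect of interest.** Hypothesis 1 is worded as a difference over time. The Power Analysis describes a design "where the slope is the dependent measure", with a group difference that starts at 0 at baseline.
- **Imbalance rule.** The initial stage says: "Any variables on which the groups differ initially will be explored as covariates in subsequent analyses". The final stage says that, if needed, "baseline covariates (e.g., demographics) will also be added to the model". The Hypothesis 1.1-1.3 analysis gives the criteria: imbalance at p < 0.10, and those variables also "moderately associated with the outcome (p < 0.15) will be included as covariates in the model".

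No covariate-by-time term is named for Hypothesis 1. Interactions are named for the moderators in Exploratory Aim 3.

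**The concern.** The issue is how the covariates enter the model, not how they are selected. A baseline covariate entered in the ordinary way has a single coefficient that applies equally at every visit, baseline included. The treatment effect is a contrast of changes from baseline, and a shift common to all visits drops out of it. The analyst would follow the rule, the report could call the result adjusted, and the Hypothesis 1 estimate would be the unadjusted one.

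Two things are at stake. If a variable that predicts change in SI-R is unbalanced by chance, its contribution to the group difference in change stays in the estimate. And any precision that such a variable could add is not gained.

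**Working it through.** The plan gives no figure for this point. The check is algebra, then fitted models, then an illustration of size.

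**Inputs from the documents.** 68 per arm; 7 visits including baseline; SI-R SD about 12.8; correlations .45 to .70; autoregressive covariance; 15% drop-out; target difference 0.5 SD, i.e. 0.5 x 12.8 = 6.4 points (all Power Analysis). Imbalance threshold p < 0.10 (Hypothesis 1.1-1.3).

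**Assumptions.** An effect of the covariate on SI-R change of 0.2-0.4 SD per SD; equally spaced visits for the autoregressive case; a continuous covariate with a normal-approximation test.

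**1. Algebra.** Let the mean for arm g at visit t be m(g,t) + c·X. With complete data, for any common within-subject covariance, the fitted m(g,t) is the arm's visit mean minus c times the arm's mean of X. The change contrast is

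[m(1,t) − m(1,0)] − [m(0,t) − m(0,0)].

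The term in c appears with both signs in each bracket and vanishes. The same holds for a linear slope, because a constant shift moves only the intercept. If the coefficient may differ by visit, c(t), the contrast is reduced by [c(t) − c(0)] x (difference in arm means of X). That is the amount by which imbalance distorts change. It is zero when X relates only to level, since then c(t) = c(0).

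**2. Fitted models, complete data.** Simulated trials, 68 per arm:

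| Fit | No X | X main effect | X by time |
|---|---|---|---|
| Session-26 contrast, constant correlation (SD units) | 0.2090 | 0.2090 | 0.1111 |
| Session-26 contrast, AR(1) (SD units) | 0.2048 | 0.2048 | 0.1028 |
| Random intercept and slope, REML: slope | 1.95392 | 1.95392 | 1.501 |
| REML, saturated last-visit contrast | 1.11934 | 1.11934 | 0.589 |

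In the first two rows the imbalance was 0.30 SD and the effect on change 0.3, so the expected distortion is 0.30 x 0.3 = 0.09. The interaction removed 0.098 and 0.102. In the REML example the main effect of X moved only the group main effect (0.598 to 0.033). At a given covariance it also left the standard error unchanged (0.1328 both ways, constant correlation).

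**3. Drop-out of about 15%.** Cancellation is approximate. The mean estimate moved by at most 0.03 SI-R points; single simulated trials moved by up to about 0.9 points, against a standard error of about 3.0.

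**4. Size of what remains.**

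- Threshold imbalance: 1.645 x sqrt(2/68) = 0.282 SD.
- Mean imbalance when triggered: 2.06 x sqrt(2/68) = 0.354 SD.
- Residual distortion: 0.354 x 0.2 = 0.07 SD to 0.354 x 0.4 = 0.14 SD. Times 12.8, this is 0.9 to 1.8 SI-R points, or 14-28% of the 6.4-point target.

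**5. Conditional false-positive rate at that imbalance.** With d the residual distortion and SE = SD of change x sqrt(2/68), the rate is Φ(−1.96 + d/SE) + Φ(−1.96 − d/SE).

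- Constant correlation: SD of change = sqrt(2(1 − ρ)) = 1.049 at .45 and 0.775 at .70, so SE = 0.180 and 0.133. d/SE runs from 0.07/0.180 = 0.39 to 0.14/0.133 = 1.07. Rate: 7% to 19%.
- AR(1), session 26 (four visits after baseline): SD of change = sqrt(2(1 − ρ⁴)) = 1.385 and 1.233, so SE = 0.238 and 0.211. d/SE runs from 0.30 to 0.67. Rate: 6% to 10%.

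**The case against.** **The form of adjustment is simply unspecified.** The plan neither states nor excludes a by-time term, and it does not write out the exact contrast. That is true. But the ordinary meaning of adding a covariate is a main effect, and the plan names interactions where it wants them, in Exploratory Aim 3. If the tested effect were the group difference at a single visit, the covariate would act, though with one coefficient common to all visits. That would be the wrong amount for a variable whose effect changes over time. The hypothesis and the Power Analysis both point to change.

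**Other protection exists.** A reader might infer that the plan has no working protection and that all imbalance stays in the result. The documents do not support that. Modelling baseline as a response already removes imbalance related only to SI-R level. The initial stage also promises to consider group differences in interpretation, and Exploratory Aim 3 looks at age and baseline executive functioning with interactions.

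**No validity failure.** A reader might also infer that the Hypothesis 1 test is biased. It is not: randomization keeps the unconditional error at 5%, and an inert covariate returns that valid test.

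**The size can be overstated.** The 19% end needs an effect of 0.4 SD per SD at constant correlation .70, which is a correlation of about 0.4/0.775 = 0.52 with change. Nothing in the documents supports a value that high. At 0.1 SD per SD the rate is 5-6%. With ten independent baseline variables, at least one reaches p < 0.10 in 1 − 0.9¹⁰ = 65% of trials, but that does not mean that most trials are distorted. It covers the imbalance criterion only and ignores both the p < 0.15 criterion and the need to predict change.

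These points limit the consequence. They do not affect the cancellation.

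**Conclusion.** The point stands in limited form. On its plain reading, the stated covariate adjustment cannot act on the group-by-time effect. This is exact with complete data and, on average, nearly exact with drop-out; it does not depend on the covariance structure or on any assumed effect size.

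What stays in the estimate is chance imbalance in variables that predict change. The 0.9-1.8 points and the conditional error rates (6-10% autoregressive, 7-19% constant correlation) illustrate the size. They rest on the assumed 0.2-0.4 SD per SD and on the mean triggered imbalance, and the autoregressive range also on equal spacing. This is a conditional distortion and a lost chance of precision, with a valid test on average: a worthwhile, inexpensive correction to the plan.

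**What to change.** In the final-stage model description and again in the Hypothesis 1.1-1.3 analysis, state that each retained baseline covariate enters as a main effect together with its interaction with visit, so that the group-by-time contrast is adjusted. The sentence should concern covariates other than baseline SI-R, which is already a response in the model. It would also help to write out the contrast that tests Hypothesis 1.

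The cost is one sentence, up to 6 extra degrees of freedom per covariate (seven visits), and a rise of about 1% in standard error for each covariate that does not predict change. If several covariates are retained, these costs add up.

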Adherence to treatment (mediator) will be measured in the following ways: (1) Number of sessions attended; (2) Therapist ratings of homework compliance (0-100%) based on written assignment review and patient report after each session. Composite adherence score will be calculated on a 10-point Likert scale ranging from 0 (Almost never/never adherent) to 10 (Always adherent).

Timeline

The first 3 months of the project are designed to hire staff, train clinicians, the blind raters, and VRAs (Table 3). There will be a total of 7 overlapping study waves, each lasting 12 months, in which we will enroll 9-10 patients. During the last 3 months of the project, we will finalize data analysis, publish the results and determine the next step for competitive funding.

Statistical Plan

Missing data will be minimized by intensive training of the raters in techniques of clarifying answers and checking questionnaires while Veteran participants are on-site. When missing values are identified, several approaches to acquire the necessary data will be employed: (1) if at all possible, Veteran participants will be rescheduled within 24 hours of completion of tests or interviews; (2) if a participant cannot be rescheduled, an effort will be made to send a tester to the individual's place of residence within the same period; (3) missing data will be examined to assess randomness. Missing data (i.e. loss to follow-up) will be tested to determine if it is informative, and the methods developed by Diggle⁸⁷ and Ridout⁸⁸ to test for completely random dropouts will be used to impute missing values. However, the primary data analysis method allows inclusion of subjects with missing data or those who terminated the study early, without relying on data imputation procedures. Furthermore, we will test whether the drop-outs are random or systematic by comparing the drop-outs with the study completers on the baseline data. The importance of missing data will be examined in the second stage of data analysis (see below).

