Dependent Variables: Hoarding severity (SI-R), Functioning (UPSA, USORT, SLOF, WHODAS 2.0) Independent Variables: Quality of life (Neuro-QoL) Statistical Analysis: The effect of mediator variables will be tested similar to the hypothesis 2.1. **Exploratory Aim 3:** To explore **age and baseline executive functioning** as moderators in order to determine subpopulations in which CREST work best. **Exploratory Aim 4:** To examine time to **maximum effect of treatment gains**.

These aims are focused on exploring on whom and under what conditions the treatment works best. These analyses may identify subpopulations with possibly different mechanisms and must be a baseline or prerandomization characteristic that could impact treatment outcome. We will focus on the moderator effect of age and baseline executive functioning and their interactions with treatment group. Age will be explored as continuous and ordinal (i.e. 45-55, 56-65, 66-75, 76-85) in format. If the interaction effect is significant, pairwise comparisons of groups will be performed. These analyses will examine interactions of group with time at each level of the moderator, and evaluate treatment within each moderator subgroup. These exploratory aims will be examined using random effects regression analyses for each candidate moderator as a main effect and in interaction, similarly to methodology used for the hypothesis testing. Furthermore, we will explore time to maximum effect of treatment gains (>35% reduction on SI-R) using survival analysis. The estimated survivorship curves will be obtained from Kaplan-Meier maximum likelihood estimates for each treatment group. The parameter estimates and 95% CI for the hazard ratio will be obtained from the Cox proportional hazards. Subjects who do not respond to treatment will be censored on their last visit date.

Power Analysis

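### Hypothesis 2.1 fits one straight SI-R slope across treatment and follow-up, which can understate mediator effects and, if early stoppers also leave assessment, weaken or even reverse the adherence effect

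*Combined protocol and SAP*

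**What the plan says.** All references are to the combined protocol and SAP.

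- **Statistical Plan, Hypotheses 2.1.** SI-R "will be used as a repeated measure for all the available time points", and then: "In essence, the slope of each outcome measure on time will be used as a dependent measure". The model is given as: "Random effects models will be used for analysis and the change score of mediators will be included in the model". There is no treatment-phase window, no break at session 26, and no rule for patients who have only early visits. Hypothesis 2.2 is to be tested in the same way.
- **Table 2.** SI-R is measured at seven visits. The last two fall 3 and 6 months after treatment has ended.
- **Statistical Plan, final stage.** "Intercept and slope will be modeled as random effects nested within subject", but also "A fully saturated treatment by time model will be utilized for inference". The analysis set needs a baseline and at least one later visit.
- **Measures, adherence.** The composite is built from "Number of sessions attended" and therapist ratings of homework. Its weights are not given, and neither component can exist before treatment starts.
- **Statistical Plan, missing data and second stage.** Early terminators stay in the analysis. Pattern-mixture models are planned in general, without mention of hypothesis 2.1. Nothing states whether a patient who stops treatment goes on being assessed.

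**The concern.** A straight line through a treatment period and an untreated follow-up describes the treatment period only if change continues at the same rate afterwards. If it slows, the line is too flat for every patient with follow-up visits, and the mediator effect read from it is too small.

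The second problem concerns adherence. A patient whose last visit is at session 13 or 21 contributes only treatment-phase visits, so that patient's line is not flattened. The same patient has attended few sessions. Low adherence and an apparently steep slope then share a cause, which works against the plan's hypothesis that adherence carries symptom reduction.

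At stake is the adherence result in hypothesis 2.1, and more generally whether the slope being explained is the effect that hypothesis 1 tests with saturated time. Separately, "the change score of mediators will be included in the model" cannot be applied to adherence as written, because adherence has no baseline to change from.

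**Working it through.** The plan gives no figure for the mediation analysis. The 80% in Power Analysis is for the between-group slope, so there is nothing of the plan's own to reproduce here.

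**1. Slopes.** Sessions are weekly (Control Group section), so the visits fall at weeks t = 0, 7, 13, 21, 26, 39, 52. For illustration, take SI-R falling in a straight line from 60 to 37 by week 26 and then staying flat. The two values appear in Power Analysis; reading them as this course is an assumption. The on-treatment rate is (37 - 60)/26 = -0.885 per week.

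Least-squares slope: b = Σ(t - t̄)y / Σ(t - t̄)².

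With all seven visits, t̄ = 158/7 = 22.57, Σ(t - t̄)² = 1993.7 and Σ(t - t̄)·min(t, 26) = 1015.0. The fitted slope is therefore 1015.0/1993.7 = 0.509 of the on-treatment rate, and b = -0.885 × 0.509 = -0.450.

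| Last visit | Slope per week | Share of on-treatment rate |
|---|---|---|
| Session 7, 13, 21 or 26 | -0.885 | 1.00 |
| 3 months | -0.635 | 0.72 |
| 6 months | -0.450 | 0.51 |

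If improvement after week 26 continues at 0.2, 0.5 or 1.0 of the earlier rate, the seven-visit share is 0.61, 0.75 or 1.00. If patients who stop at week 7, 13 or 21 hold their gain and are assessed to week 52, their shares are 0.08, 0.19 and 0.39. They then look slower than completers, not faster.

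**2. How many such patients.** The general plan's 10% dropout occurs before any post-baseline visit. Those patients have no slope and cannot produce the artefact. Power Analysis uses 15% with no timing. Two assumed cases bracket the number who leave later: 136 × (15% - 10%) = 6.8, about 7; and 136 × 15% = 20.4, about 20.

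**3. Mixed-model simulation.** Set-up: N = 136; SD 12.8; AR(1) or random intercept and slope, with covariance treated as known; gains flat after week 26; completers attend about 90% of sessions (SD 8%); stopping spread over sessions 7-25. The true effect is -1.5 SI-R points at week 26 per adherence point.

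| Setting | Straight line | Knot at week 26 |
|---|---|---|
| Stoppers still assessed | about -0.6 to -0.8 | about -1.4 to -1.7 |
| 7-20 stop and leave assessment | -0.6 to 0.0 | about -1.4 to -1.7 |

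The first row agrees with step 1: 0.509 × 1.5 = 0.76. Power was higher with the knot throughout. When stoppers leave, the effect is detected in 3-5% of trials using all visits, against 17-34% using baseline to session 26.

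With no true effect, a significant wrong-sign result appears in roughly 3-6% of trials with 7 leavers and 13-19% with 20. The nominal rate in that tail is 2.5%. Runs numbered 150 to 2,000 per setting; at 150, the standard error of a 5% rate is √(0.05 × 0.95/150) = 1.8 points, so these are approximate.

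**4. A harder case.** Here adherence is half sessions and half homework, with a modest homework effect; 10% stop at week 7, 13 or 21 and gain nothing further. Mean gain is 20 and residual SD 6. All of these are assumptions. The true coefficient at week 26 is -2.7.

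| Analysis | Stoppers leave | Stoppers assessed to week 52 |
|---|---|---|
| Separate slope per patient | +1.0 | - |
| Mixed model, linear time | -0.66 | -1.6 |
| Mixed model, saturated time | -0.84 | - |
| Mixed model, knot at week 26 | -1.5 | -2.9 |

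The knot recovers part of the loss. The rest comes from outcomes missing after stopping.

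**The case against.** A reader might infer that adherence will come out at zero or with the wrong sign as a matter of course. The documents do not support that, for these reasons.

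- **The model.** Random effects models are named, and the slope sentence can be read as a gloss on them. Slopes fitted separately for each patient, which reverse most readily, are not specified. Under a linear mixed model the usual result is attenuation with the right sign. In the step 4 set-up with a plateau, it averaged slightly positive (+0.2 to +0.3) only when homework had no effect and stoppers improved at the completers' rate.
- **Leaving assessment.** The plan calls for intent-to-treat testing, independent raters who assess in the home, and efforts to recover missed data. If stoppers are still assessed, the reversal disappears. The straight line is still too flat (-1.6 against -2.9 with the knot).
- **The plateau.** It is assumed. Exploratory Aim 4 says "we will explore time to maximum effect of treatment gains", but defines this as time to a reduction above 35%, which does not imply levelling at session 26. Power Analysis itself assumes that the group difference grows linearly to the last visit. Full continuation of gains would remove the problem; partial continuation only shrinks it.
- **Rescaling.** With complete data the flattening is close to a change of scale: 0.450 × 52 = 23.4, near the true 23-point fall. The one-year total survives, but the treatment-phase effect is misstated and power is lost.
- **Scope.** Homework used alone is less affected (about -0.45 against a true -0.75). Follow-up is relevant to mechanism, since the protocol expects cognitive training to help prevent relapse. The hypothesis 1 comparison of SI-R is untouched.
- **Pattern-mixture models.** They address dropout generally, but are not tied to hypothesis 2.1 and do not alter its slope.

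These points make the adherence reversal conditional. They do not reconcile the single slope with the saturated model, or justify the single slope if gains slow after treatment.

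**Conclusion.** The point holds in conditional form. As written, hypothesis 2.1 rests on one slope over treatment and follow-up, in tension with the saturated time model used for inference.

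- **If gains slow after session 26**, mediator effects on the treatment phase are understated even with full assessment: roughly half their size under a complete plateau (share 0.51), less if improvement partly continues (0.61 to 0.75).
- **If some patients also leave assessment after a post-baseline visit**, the adherence effect is weakened further and in some settings reversed. The excess of significant wrong-sign results is small with 7 such patients and material with 20.

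The plateau, the 7-20 range and the stopping pattern are all assumptions; the documents give none of them. The missing baseline for adherence needs no such assumption, but is only a clarification. This should be changed before analysis; it does not threaten the primary comparison.

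**What to change.** In Statistical Plan, Hypotheses 2.1:

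1. Replace the single slope with a piecewise-linear random effects model with a knot at session 26. Let the mediator act on the treatment-phase segment and report the follow-up segment separately as maintenance. All visits are kept. Restricting the slope to baseline through session 26 is a simpler route to the same treatment-phase quantity.
2. State how this model relates to the saturated treatment-by-time model, and carry the wording to Hypothesis 2.2.
3. Enter adherence as a cumulative level; keep change scores for mediators that have a baseline.
4. Apply the planned pattern-mixture sensitivity analysis to hypothesis 2.1 by name, and state whether patients who stop treatment continue to be assessed. The knot does not remove bias from outcomes missing after stopping.

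The cost is SAP wording and one more time term. The treatment-phase estimate makes less use of the 3- and 6-month values, and power to detect an adherence effect of the size simulated stays low (17-34% when stoppers leave).
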